11.3.2 Amenorrhea, Suppression and Control of Bleeding

11.3.2.1 Amenorrhea

The number and percentage of subjects who achieved amenorrhea will be calculated for each analysis group. Amenorrhea analysis will include subjects on study drug for at least 38 days in this extension study. For each subject, amenorrhea is defined as having 0 days of bleeding or spotting during the last 28 days of treatment with the interval starting from Study Day 11. If a subject did not have evaluable AH data during the last 28 days and no bleeding or spotting or "There was no visible blood on the sanitary products" was indicated on UBQ, then she is considered amenorrheic.

For subjects initially randomized to placebo in the pivotal Study M12-815 or Study M12-817, time to amenorrhea is defined as the number of days from the first study drug dose date to the day a subject achieving cumulative amenorrhea (i.e., the day a subject achieving amenorrhea – the first study drug dose date + 1). For a subject who achieved amenorrhea, the day she achieved amenorrhea is defined as the next day of the

CODVIE Elagolix (ABT-620)

Elagolix (ABT-620) M12-816 – Statistical Analysis Plan Version 2.0 – 24 May 2018

last bleeding/spotting day during the Treatment Period. The median, Q1, and Q3 of time to amenorrhea will be calculated using Kaplan-Meier method.

In the monthly analysis of bleeding for amenorrhea, the numerator is the number of subjects on treatment who did not bleed during the specified time window (but may have begun bleeding thereafter) and the denominator includes subjects on drug for the full window. For the final visit, the denominator includes subjects with at least 38 days on study drug.

Time Interval	Amenorrheic Status
Month 1 (Days 1 – 28)	Subject did not bleed during Study Days 1 – 28
Month 2 (Days 29 – 56)	Subject did not bleed during Study Days 29 – 56
Month 3 (Days 57 – 84)	Subject did not bleed during Study Days 57 – 84
Month 4 (Days 85 – 112)	Subject did not bleed during Study Days 85 – 112
Month 5 (Days 113 – 140)	Subject did not bleed during Study Days 113 – 140
Month 6 (Days 141 – 168)	Subject did not bleed during Study Days 141 – 168
Final Month (last 28 days of treatment)	Subject did not bleed during the last 28 days of treatment

Table 8.Monthly Analysis of Bleeding for Amenorrhea

Incidence and cumulative incidence of amenorrhea by last bleeding/spotting day at each month will be reported using the categories specified in in Table 9.

The summary will be provided in the following 2 ways: (1) including only subjects who have at least 168 days on study drug in the extension study. The denominator includes subjects who have at least 168 days on study drug in the extension study for all windows. (2) LOCF: including all subjects who have at least 38 days on study drug in the extension study. If a subject meets the criteria for amenorrhea but discontinues, this subject's

amenorrheic status was carried forward to the time points after the subject has discontinued study drug. The denominator includes subjects who have at least 38 days on study drug in the extension study.

Plots will be provided by analysis group for percentage of subjects with incidence and cumulative incidence of amenorrhea during the Treatment Period, respectively.

Analysis	Time Interval	Numerator Calculation
Incidence	Month 2 (≤ Study Day 56)	Last bleeding/spotting day occurred during Study Days 1 – 28
	Month 3 (Study Day 57 – 84)	Last bleeding/spotting day occurred during Study Days 29 – 56
	Month 4 (Study Day 85 – 112)	Last bleeding/spotting day occurred during Study Days 57 – 84
	Month 5 (Study Day 113 – 140)	Last bleeding/spotting day occurred during Study Days 85 – 112
	Month 6 (Study Day 141 – 168)	Last bleeding/spotting day occurred during Study Days 113 – 140
Cumulative	Month 2 (≤ Study Day 56)	Last bleeding/spotting day occurred before Study Day 29
	Month 3 (Study Day 57 – 84)	Last bleeding/spotting day occurred before Study Day 57
	Month 4 (Study Day 85 – 112)	Last bleeding/spotting day occurred before Study Day 85
	Month 5 (Study Day 113 – 140)	Last bleeding/spotting day occurred before Study Day 113
	Month 6 (Study Day 141 – 168)	Last bleeding/spotting day occurred before Study Day 141

Table 9.Categorical Summary of Incidence and Cumulative Incidence of
Amenorrhea by Last Bleeding/Spotting Day

11.3.2.2 Suppression of Bleeding

Suppression of bleeding is defined similarly to amenorrhea as in Section 11.3.2 except that spotting is allowed. For each subject, achieving suppression of bleeding is defined as having 0 days of bleeding during the last 28 days of treatment with the interval starting

from Study Day 11. The suppression of bleeding analysis will include subjects with at least 38 days on study drug in the extension study. If a subject did not have evaluable AH data during the last 28 days and no bleeding was indicated on UBQ ("Subject only has spotting that did not require the use of sanitary products" or "There was no visible blood on the sanitary products" was allowed), then the subject is considered having achieved suppression of bleeding. The number and percentage of subjects achieving suppression of bleeding will be summarized by analysis group.

For subjects initially randomized to placebo in the pivotal Study M12-815 or Study M12-817, time to suppression of bleeding is defined as the number of days from the first study drug dose date to the day a subject achieving suppression of bleeding (i.e., the day a subject achieving suppression of bleeding – the first study drug dose date + 1). For a subject who achieved suppression of bleeding, the day she achieved suppression of bleeding is defined as the next day of the last bleeding day during the Treatment Period. The median, Q1, and Q3 of time to suppression of bleeding will be calculated using Kaplan-Meier method.

Monthly analysis of bleeding for suppression of bleeding, incidence and cumulative incidence of suppression of bleeding by last bleeding day will be provided in the same way as was done for amenorrhea in Table 8 and Table 9. Plots will be provided by analysis group for percentage of subjects with incidence and cumulative incidence of suppression of bleeding during the Treatment Period, respectively.

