### **Unscheduled Visit**

In the event an **Unscheduled Visit** is necessary during the Treatment or Post-Treatment Follow-Up Period, the site will perform at minimum, the UBQ and an assessment of adverse events and concomitant medications. For **Unscheduled Visits** when study drug is dispensed (e.g., to replenish lost or damaged study drug), the subject will also be required to have a negative urine pregnancy test result prior to dispensing. Clinical judgment should dictate when other safety assessments (such as vital signs and/or symptom-directed physical examination) should be conducted and should also support the reason for the **Unscheduled Visit**.

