7.6.1.1 Observed MBL Volume Over a Window

If there were observed AH data between two study visits (Product Collection Visit or site visit with UBQ completed), then the MBL volume on the days with observed AH data will be the observed AH data and the MBL volume for the rest of days between the two study visits will be imputed as 0 by AH data.

UBQ responses indicate if a subject has any bleeding or spotting since the last study visit (Product Collection Visit or site visit with UBQ completed). If observed evaluable AH data is available over a window, then the UBQ will not be considered.

If the AH data is reported as "NVB" (no visible blood, discarded without assay), "NO BLEED" (no collection due to no bleeding as indicated by subject or clinical site on assay requisition form), or "TL BQL" (total below low limit of quantitation), the numeric value for the AH data will be imputed as 0. If the AH data is reported as other character value ("NULL," "IN ERROR," "NO DATA," and etc.), the corresponding numeric value for the AH data will be set as missing.

The observed MBL volume over a window (such as the Final Month, Month 1 [Study Days 1 – 28], Month 2 [Day 29 – Day 56], Month 3 [Day 57 – Day 84], Month 4 [Day 85 – Day 112], Month 5 [Day 113 – Day 140], and Month 6 [Study Days 141 – 168]) is defined as follows:

- If a subject has any evaluable AH data reported in the window, then the subject's MBL volume in this window will be the total combined observed AH data of validated and non-validated sanitary products over this window.
- If a subject is missing AH data or all AH data are unevaluable in the window and the UBQ is completed and indicates no bleeding or spotting, "Subject only had spotting that did not require the use of sanitary products" or "There was no visible blood on the sanitary products" and covers this window, then:
 - $\circ~$ A value of 0 will be assigned to the MBL volume over this window.
- If a subject is missing AH data or all AH data are unevaluable in the window and the UBQ is completed with no bleeding or spotting or "Subject only had spotting that did not require the use of sanitary products" or "There was no visible blood on the sanitary products" indicated but UBQ does not cover the full window, then:
 - A value of 0 will be assigned to the MBL volume over this window if the days not covered by UBQ response as described above have AH imputed MBL volume (see first paragraph in Section 7.6.1.1) being 0 for those days.

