11.3 Secondary and Other Efficacy Analyses

Secondary efficacy endpoints during the Treatment Period include the following:

- Change and percent change from Baseline in MBL volume to each month and to the Final Month;
- Percentage of subjects with suppression of bleeding (no bleeding allowed, spotting allowed) at the Final Month;
- Percentage of subjects with Baseline hemoglobin ≤ 10.5 g/dL who have an increase in hemoglobin > 2 g/dL at Month 6.

Other efficacy endpoints during the Treatment Period include the following:

- Percentage of subjects with MBL volume < 80 mL and 50% or greater reduction in MBL volume from Baseline during 28-day intervals throughout the Treatment Period;
- Percentage of subjects with amenorrhea;
- Percentage of subjects with control of bleeding;
- The number of bleeding days;
- Change and percent change from Baseline in hemoglobin concentration;
- Patient Global Impression of Change (PGIC) questionnaire for Menstrual Bleeding and Non-Bleeding Uterine Fibroid Symptoms;

- Change and percent change from baseline in fibroid and uterine volume;
- Change from baseline for the UFS-QoL;
- Change from baseline for the EuroQoL-5D (EQ-5D-5L);
- The Health Care Resource Utilization (HCRU) questionnaire;
- Change from baseline for the WPAI.

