11.3.3 Bleeding Days

The numbers of bleeding days by intensity categories (Section 7.6.2) will be calculated for each 28-day interval starting at Study Day 1 up to Study Day 168 in the Treatment Period (i.e., Study Days 1 - 28, Study Days 29 - 56, Study Days 57 - 84, Study Days 85 - 112, Study Days 113 - 140, and Study Days 141 - 168) and the first 28-day interval in the Post-Treatment Follow-up Period (i.e., Study End Days 1 - 28) for each analysis group. For each 28-day interval, each analysis includes subjects who did not premature discontinue in or before this 28-day interval. For example, for Study Days 29 - 56, it includes subjects who were on treatment for at least 56 days in the extension study. For Final Month analysis, it includes subjects who were on treatment for at least 38 days in the extension study. The summary of average number of bleeding days in a 28 day window during the Treatment Period will be provided for each analysis group by intensity categories.

If a subject did not have evaluable AH data during an interval and no bleeding was indicated on UBQ ("Subject only has spotting that did not require the use of sanitary products" or "There was no visible blood on the sanitary products" was allowed), then the number of bleeding days over the interval is 0. The number and percentage for each analysis group and overall will be provided for subjects who did not have evaluable AH data during an interval and bleeding was indicated on UBQ.

The change and percent change from Baseline in the numbers of bleeding/spotting days and bleeding days to each 28-day interval and Final Month in the Treatment Period and the first 28-day interval in the Post-Treatment Follow-up Period will be summarized for each analysis group, respectively.

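### A negative bleeding questionnaire that does not cover all 28 days can count as suppression of bleeding, although SAP 7.6.1.1 would set the same woman's blood loss to missing

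*SAP*

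**What the plan says.** SAP 11.3 lists as a secondary endpoint "Percentage of subjects with suppression of bleeding (no bleeding allowed, spotting allowed) at the Final Month". It places "Percentage of subjects with amenorrhea", control of bleeding and the number of bleeding days among the other efficacy endpoints.

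Each of these has a fallback for a woman with no evaluable AH data in the window:

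- **Suppression (11.3.2.2):** "If a subject did not have evaluable AH data during the last 28 days and no bleeding was indicated on UBQ", with spotting-only and no-visible-blood answers allowed, "then the subject is considered having achieved suppression of bleeding".
- **Amenorrhea (11.3.2.1):** if the absence of bleeding or spotting, or of visible blood, "was indicated on UBQ, then she is considered amenorrheic".
- **Control of bleeding (11.3.2.3):** the same evidence gives success. A further sentence says that a UBQ reporting bleeding or spotting means the criterion is not met.
- **Bleeding days (11.3.3):** "If a subject did not have evaluable AH data during an interval and no bleeding was indicated on UBQ", the count for that interval is 0.

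SAP 7.6.1.1 uses the same questionnaire for MBL volume, but on conditions. A qualifying UBQ gives 0 mL if it covers the window. Where a negative answer is "indicated but UBQ does not cover the full window", the value is 0 only if the remaining days have AH-imputed zeros. Failing both, the volume is missing. The same section says that a UBQ reports on the time since the last Product Collection Visit or site visit with a UBQ, not on a fixed 28 days.

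**The concern.** Suppression, amenorrhea and control are statements about every day of a 28-day window, apart from the one spotting day that control allows. A questionnaire reaching back only part of the window cannot establish them. The SAP recognises this for MBL volume but not in the four sections that use the same questionnaire for bleeding status. The same 28 days can therefore be unknown for blood loss and a confirmed success for a secondary endpoint. The clause can only turn unknown status into success or zero bleeding days, never the reverse. It acts on women whose product collection, assay or attendance failed.

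**Working it through.** The documents give no figure to reproduce. The check sets the two rules side by side and asks when they disagree.

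**1. The rules when no AH data are evaluable in the window**

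| SAP section | Result from a qualifying UBQ | Coverage condition | If the condition fails |
|---|---|---|---|
| 7.6.1.1 MBL volume | 0 mL | UBQ covers the window, or uncovered days are AH-imputed 0 | Missing |
| 11.3.2.1 Amenorrhea | Amenorrheic | None stated | Not addressed |
| 11.3.2.2 Suppression | Achieved | None stated | Not addressed |
| 11.3.2.3 Control | Achieved | None stated | Not addressed |
| 11.3.3 Bleeding days | 0 days | None stated | Not addressed |

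They disagree only if there is a qualifying UBQ, no evaluable AH data in the window, and at least one day covered by neither a qualifying UBQ nor an AH-imputed zero.

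**2. Case A: an earlier keg could not be assayed**

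Inputs: the UBQ is completed only when no keg is returned (Protocol Appendix C, Treatment Period, footnote m). AH results such as IN ERROR are set to missing (SAP 7.6.1.1). The dates are illustrative.

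- Month 5 visit on Day 140; last dose and Month 6 visit on Day 168. The Final Month is Day 168 − 27 = Day 141 to Day 168.
- She bleeds early in the window and returns a keg at a Product Collection Visit on Day 150. The result is IN ERROR. No UBQ is done, because a keg was returned.
- On Day 168 she truthfully reports no bleeding since that visit. The UBQ covers Days 151–168, which is 168 − 150 = 18 days. Uncovered: 28 − 18 = 10 days.
- There are no observed AH data between Days 140 and 150, so zeros cannot be imputed for those 10 days.

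MBL volume is missing under 7.6.1.1. Under 11.3.2 she is amenorrheic, suppressed and controlled, and under 11.3.3 a Final Month count would be 0 bleeding days. Products are collected on days with bleeding or spotting (Protocol 5.3.1.1), so the uncovered days are the ones most likely to contain bleeding. The extra sentence for control does not catch her, because no UBQ records bleeding.

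**3. Case B: no report reaches the last dose after an early stop**

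- Last UBQ, negative, on Day 140; last dose on Day 160; nothing later. The Final Month is Day 160 − 27 = Day 133 to Day 160.
- Covered: Days 133–140, which is 140 − 133 + 1 = 8 days. Uncovered: 28 − 8 = 20 days.

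MBL volume is missing, yet the bleeding-status rules give success. The cumulative amenorrhea summary with last observation carried forward then takes amenorrheic status beyond discontinuation, and 11.3.2.2 applies the same approach to suppression.

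**4. Case C: two UBQs in the window disagree**

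An earlier UBQ reports bleeding with products not collected, and a later one is negative. Control of bleeding is protected by its extra sentence. Amenorrhea and suppression do not say which UBQ prevails.

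**5. Effect on a reported rate**

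Let p be the share of women affected and r the rate among the others.

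- SAP rule as written: r(1 − p) + p
- Affected women set to missing: r
- Affected women counted as not achieved: r(1 − p)

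The excess over missing is p(1 − r); the excess over not achieved is p. The documents give neither p nor r. As scale only, at an assumed r of 60%, each 1% of women affected adds 0.01 × 0.40 = 0.4 points over missing and 1 point over not achieved. At assumed r of 50% and 70% the first figure is 0.5 and 0.3 points.

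**The case against.** The strongest case against is that follow-up is nearly continuous. At each treatment-period site visit a woman either returns a keg or has a UBQ, so a woman who attends and collects as planned has every day reported.

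A reader might infer that the visit windows alone open a gap: with Month 5 four days late and Month 6 four days early, the visits are 28 − 4 − 4 = 20 days apart, which seems to leave 8 of the 28 days uncovered. The documents do not support this. With visits on Days 144 and 164 and last dose on Day 164, the Final Month is Days 137–164. The Month 6 UBQ covers Days 145–164. The Month 5 UBQ or AH report covers the 8 earlier days, because it reaches back to Month 4, at the latest Day 112 + 4 = 116. A missed Month 5 visit lengthens the look-back, to at least 164 − 116 = 48 days. Nor do unscheduled visits, where "the site will perform at minimum, the UBQ and an assessment of adverse events and concomitant medications", create a gap: an extra UBQ splits the recall period, and the preceding report still covers the preceding days.

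Three further points have weight. Protocol 5.4.1 and Appendix C call for a Premature Discontinuation Visit with a UBQ, so case B needs that visit to be absent or late. In case C, a woman who reported bleeding does not naturally fit a definition requiring no bleeding days, and a careful programmer might fail her. The SAP is silent on coverage rather than waiving it.

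What remains is that the SAP states the condition once and omits it in four sections using the same instrument. Two programmers could report different results for a secondary endpoint, and case A follows the stated rules exactly.

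**Conclusion.** The inconsistency is real and the affected group is narrow: women with no evaluable AH data in the window, a negative UBQ, and days left open by a failed assay, a missing end-of-treatment report or an earlier positive UBQ without products. A reader might infer that every woman with missing MBL volume becomes a success. She does not: a woman with no UBQ, or only one saying that products were forgotten or discarded, is not made a success by these clauses.

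The bias runs only towards success. Its size cannot be derived from the documents, and any percentage for the share affected would be an assumption. The primary endpoint is not touched, because SAP 11.2.2 derives it from MBL volume under 7.6.1.1. SAP 11.1 plans no efficacy tests, so the consequence is overstated descriptive percentages, not a false positive. Correction is still worthwhile, because it changes a stated rule for a secondary endpoint and needs no new data.

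**What to change.** In SAP 11.3.2.1, 11.3.2.2, 11.3.2.3 and 11.3.3:

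- Accept UBQ evidence only under the 7.6.1.1 coverage rule: every day in the window is covered by a qualifying UBQ or an AH-imputed zero. Keep each section's own list of qualifying answers, since spotting-only counts for suppression but not for amenorrhea or control.
- Otherwise set the status, or the number of bleeding days, to missing, in line with MBL volume, and say that these women leave the denominator. This also settles case C, because days under a positive UBQ are not covered by a qualifying one.
- Leave the extra sentence in 11.3.2.3 as it is. It concerns reported bleeding, so it is no precedent for failing women whose days were unobserved.
- For suppression, amenorrhea and control, add a sensitivity summary counting the uncovered women as not achieved.
- Report the number of uncovered women by analysis group for each of the four measures.

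The cost is one cross-reference in each of four sections, one extra summary and a count. A few women lose success status. No further data collection is needed.

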11.3.2.3 Control of Bleeding

For each subject, achieving control of bleeding is defined as having 0 days of bleeding and up to 1 day of spotting during the last 28 days of treatment with the interval starting from Study Day 11. The control of bleeding analysis will include subjects with at least 38 days on study drug in the extension study. If a subject did not have evaluable AH data during the last 28 days and no bleeding or spotting or "There was no visible blood on the sanitary products" was indicated on UBQ, then the subject is considered having achieved

control of bleeding. If the subject indicates bleeding or spotting on the UBQ, the subject does not meet the criteria for control of bleeding.

The number and percentage of subjects achieving control of bleeding will be summarized by analysis group.

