Appendix F. Uterine Bleeding Questionnaire (UBQ) – Treatment Period – SAMPLE

Version 2.0

During site visits in the Treatment Period, subjects who **did not** return a Sanitary Product Collection Keg (for menstrual blood loss analysis) will be asked whether they had any uterine bleeding or spotting since their last study visit.

• Did the subject have any bleeding or spotting since her last study visit?

 \Box No \Box Yes

If yes, why were sanitary products not collected/returned? (Please select one response)

- □ Subject only had spotting that did not require the use of sanitary products*
- $\hfill\square$ There was no visible blood on sanitary products*
- □ Subject forgot to/did not collect*
- □ Subject/Site discarded the sanitary products*
- □ Subject is still bleeding/spotting; will return when bleeding/spotting complete
- □ Subject collected sanitary products and did not bring them to this visit; will return sanitary products at a later date
- \Box Other
- * If this response is checked, remind subject to collect and return all used or worn sanitary products with or without visible blood.

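### SAP 11.3.2.3 scores one UBQ answer, bleeding or spotting reported but no visible blood on the products, as both achieving and failing control of bleeding

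*SAP*

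**What the plan says.** SAP 11.3.2.3 gives the day-count definition: "control of bleeding is defined as having 0 days of bleeding and up to 1 day of spotting", over the last 28 days of treatment, among subjects with at least 38 days on study drug. It then covers subjects with no evaluable AH data in that interval. Such a subject has control if the UBQ shows no bleeding or spotting, or shows "There was no visible blood on the sanitary products". The closing sentence of that paragraph reads: "If the subject indicates bleeding or spotting on the UBQ, the subject does not meet the criteria for control of bleeding". It contains no exception.

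The UBQ in SAP Appendix F (same layout in Protocol Appendix D) opens with one No/Yes question: "Did the subject have any bleeding or spotting since her last study visit". A list of seven reasons follows under "If yes, why were sanitary products not collected/returned". No visible blood on the products is one of those seven.

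SAP 11.3.2.1 defines amenorrhea as no bleeding and no spotting days in the same 28 days, with the same 38-day requirement. It counts the no-visible-blood answer as amenorrheic when there are no evaluable AH data, and has no sentence that takes this back.

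SAP 7.6.1.1 says of AH data and the questionnaire: "If observed evaluable AH data is available over a window, then the UBQ will not be considered".

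**The concern.** The no-visible-blood response cannot be given without first answering Yes to bleeding or spotting. A woman who gives it has therefore, on the face of the form, indicated bleeding or spotting. One sentence of 11.3.2.3 passes her and the next fails her, and the SAP does not say which prevails.

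Two programmers working from this text could report different control rates. One who applies the last sentence as written would also produce women who are amenorrheic yet lack control of bleeding. Amenorrhea is the stricter condition, so that combination is a derivation error and would undermine any side-by-side reading of the two endpoints.

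**Working it through.** There is no stated figure to reproduce. The check compares the rules.

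**1. Are the definitions nested?** Let b be the number of bleeding days and s the number of spotting days in the 28-day interval.

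- Amenorrhea: b = 0 and s = 0.
- Control: b = 0 and s ≤ 1.

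Every pair (b, s) that satisfies the first satisfies the second. Enumerating all pairs with b + s ≤ 28 gives 0 patterns that are amenorrheic but not controlled. Both analyses use the same interval and the same 38-day requirement, so amenorrheic subjects must be a subset of controlled subjects.

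**2. How is each UBQ answer scored when there are no evaluable AH data?** There are 8 possible answers: No, plus 7 reasons under Yes. An entry of no under amenorrhea or suppression means that the UBQ rule does not award success.

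| UBQ answer | Amenorrhea (11.3.2.1) | Suppression (11.3.2.2) | Control awarded by 11.3.2.3 | Control denied by last sentence, read literally |
|---|---|---|---|---|
| No | yes | yes | yes | no |
| Yes, spotting only | no | yes | no | yes |
| **Yes, no visible blood** | **yes** | **yes** | **yes** | **yes** |
| Yes, products not collected | no | no | no | yes |
| Yes, products discarded | no | no | no | yes |
| Yes, still bleeding | no | no | no | yes |
| Yes, will bring later | no | no | no | yes |
| Yes, other | no | no | no | yes |

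Exactly 1 of the 8 answers is both awarded and denied control. It is also the only answer that gives amenorrhea together with denied control. With an exception for this answer in the last sentence, conflicts fall from 1 of 8 to 0 of 8.

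**3. Do neighbouring sections handle the answer?** Yes. Suppression (11.3.2.2), bleeding days (11.3.3) and post-treatment menses (11.3.5.4) each say in parentheses how this answer is treated when deciding whether the UBQ shows bleeding. The last sentence of 11.3.2.3 does not.

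**4. How large can the effect be?** Let N be the subjects with at least 38 days on drug, A the amenorrheic subjects, S those with no bleeding days and exactly 1 spotting day, and k the subjects without evaluable AH data who gave the no-visible-blood answer.

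- Control rate, answer scored as achieved: (A + S) / N.
- Control rate, last sentence applied literally: (A + S − k) / N.
- Difference: −k / N, so each 1% of N in this position lowers the rate by 1 percentage point.
- The literal control rate falls below the amenorrhea rate A / N only if k > S.

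The documents give neither k nor S.

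**The case against.** The best defence is that a specific rule governs a general one. 11.3.2.3 names the no-visible-blood answer as a success, so the next sentence would naturally cover the remaining Yes answers. That reading gives it a purpose: it fails the spotting-only answer, which suppression allows, because the UBQ cannot count spotting days and control permits at most one. The SAP also treats the answer as non-bleeding elsewhere: 0 mL in 7.6.1.1, amenorrhea in 11.3.2.1, suppression in 11.3.2.2, and no bleeding days in 11.3.3. Letting the last sentence prevail would leave the no-visible-blood words in 11.3.2.3 with no effect.

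This is very probably the intended reading, and it removes the conflict. What stands against it is that the SAP does not state this precedence, while three neighbouring sections spell out the handling.

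A reader might go further and infer that the last sentence overrides AH-based scoring, because it does not repeat the no-AH condition. An example would be a woman who reports that she is still bleeding and later returns products that are assayed. The documents do not support that inference. The sentence directly follows one limited to subjects without evaluable AH data, and 7.6.1.1, within the section that covers both blood-loss volume and bleeding days, sets the UBQ aside when evaluable AH data exist. That rule is written for observed volume over a window, so its application to control is implied rather than spelled out.

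**Conclusion.** The inconsistency is real but narrow. It concerns one UBQ answer, among subjects with no evaluable AH data in the last 28 days and at least 38 days on drug. The impossible result, amenorrheic but not controlled, arises only if the last sentence of 11.3.2.3 is programmed literally. The effect on the control rate is then −k / N and can only be downward.

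The size is unknown. A reader might put a figure of several points on it, or conclude that the control rate will be reported below the amenorrhea rate. Neither follows: the documents give no frequency for this answer, and the second result needs the misclassified women to outnumber those with exactly one spotting day.

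Control of bleeding is listed among the other efficacy endpoints in SAP 11.3 and is summarised without tests (SAP 11.1). The primary endpoint and the secondary blood-loss endpoint use 7.6.1.1, which sets this answer to 0 mL. Suppression states its own handling, and the hemoglobin endpoint does not use the UBQ. None of these is affected. This is a minor correction, worth making because it removes an avoidable programming error.

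**What to change.** Replace the last sentence of SAP 11.3.2.3 with wording such as: *A subject with no evaluable AH data in the interval whose UBQ reports bleeding or spotting, with any response other than* "There was no visible blood on the sanitary products"*, is counted as not having control of bleeding.* The exception removes the conflict and still fails the spotting-only answer. The no-AH condition only makes explicit what 7.6.1.1 already implies.

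Add a programming check that every subject counted as amenorrheic at the Final Month is also counted as having control of bleeding.

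The cost is one sentence and one check. No new data are needed, because the form already records the reason given under Yes.
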